## **Blinding of outcome evaluators**

Outcome evaluators will be masked (blinded) and not involved with the study. The statisticians who will conduct the analyzes will also be masked to the treatment status until the analyzes are completed. Due to the types of interventions, it will not be possible to mask the participants and providers of the intervention.

## **Intervention**

Patients included in the study will undergo one of two possible interventions: open rotator cuff repair (1) or arthroscopic rotator cuff repair (2).

## **Team**

Five surgeons with at least 03 years of surgical technique experience will participate of this study: [name] [name], group leader and specialist in shoulder and elbow surgery since 1983; [name] [name], medical doctor graduated from UNICAMP/Sao Paulo (State University os Campinas) in 1999, with a residency in Orthopedics and Traumatology from UNIFESP (Federal University of Sao Paulo) in 2003 and specialist in shoulder and elbow surgery from Santa Casa de São Paulo in 2005; [name], medical

doctor graduated from UNIFESP (Federal University of Sao Paulo) in 2008, residency in Orthopedics and Traumatology from UNIFESP between 2009 and 2012, specialist in shoulder and elbow surgery from UNIFESP in 2013; [name] [name], medical doctor from USP (State University of Sao Paulo) between 2008 and 2013, residency in Orthopedics and Traumatology from USP between 2010 and 2013, specialized in shoulder and elbow surgery from USP in 2014; [name], medical doctor graduated from USP in 2011, residency in Orthopedics and Traumatology from USP between 2012 and 2015, specialist in shoulder and elbow surgery from USP in 2016. Also, may be part of the project and participate in surgeries the residents of shoulder and elbow surgery from Hospital Alvorada Moema, as well as the residents of Orthopedics and Traumatology at this hospital. In addition, residents in shoulder and elbow surgery at Albert Einstein Hospital will participate in the study.

As with patient randomization, surgeons will be randomized; it will be done by computer software (<http://www.randomizer.org>), where each surgeon will be assigned a number from 1 to 5. This will be attached to the patient's envelope and the responsible surgeon will be revealed prior to the intervention, immediately after application of anesthetic technique.

### **Anesthetic Technique**

All patients will undergo balanced general anesthesia (inhalatory and intravenous) without brachial plexus block. At the end of the procedure, 20 milliliters of local anesthetic will be administered in the subacromial space.

### **Open rotator cuff repair**

Patients will be positioned in a beach chair position with the affected limb pending off the table, allowing manipulation and full range of motion range. After asepsis, antisepsis and placement of sterile surgical fields, anterolateral incision will be made in the shoulder in question; the deltoid muscle belly will be gently divided along its fibers until exposure of the subdeltoid / subacromial bursa, which will be partially excised for exposure of the subacromial space and rotator cuff tendons. After mobilization and release of the ruptured tendons and debridement of the rotator cuff footprint, the tendon repair to the bone will be performed using 5.5m metal anchors, according to the preference and technique

chosen by the surgeon. In all cases, the release of the coracoacromial ligament and acromioplasty will be performed.

### **Arthroscopic Rotator Cuff Repair**

The patients will be positioned in lateral decubitus position, with the limb to be operated attached to a skin traction device, which through a traction post and 07 kilograms (kg), will maintain the shoulder in the following position: abduction of 30 to 60 degrees and flexion of 20 to 30 degrees. After asepsis, antisepsis and placement of impermeable sterile surgical fields, a posterolateral incision will be made in the shoulder for optic introduction, with a 50 mmHg pressure pump and a 0.90 flow, and inspection of the glenohumeral joint. If necessary, anterior accessory portal will be performed for intraarticular instrumentation. After joint inspection, the optic will be introduced into the subacromial space with detachment of the subacromial and subdeltoid bursa with the trocar. After visualizing the lesion, an accessory lateral portal will be performed. With the use of shaver blades, partial bursectomy will be performed and any adherence to the tendon stumps will be released, as well as debridement of the rotator cuff footprint. The tendon will then be reinserted to the bone using metallic 5.5mm anchors, according to the preference of each surgeon. The technique used, as well as the suture configuration and type of knot used will be defined by the surgeon, according to his preference. After tendon repair, the coracoacromial ligament will be released, as well as acromioplasty.

### **Postoperative rehabilitation**

All patients will undergo the same postoperative rehabilitation regimen: use of Velpeau sling for 6 weeks; pendulum exercises from the second week; active movement and recovery of the range of motion from the sixth week and strengthening from the twelfth week.

### **Primary outcomes**

The Constant-Murley Score (CM) validated for the Portuguese language (33) will be measured preoperatively at 6, 24 and 48 weeks after the intervention. The evaluators will ask the patients to fill in the validated

CM form for the Portuguese language and measure the range of motion with a goniometer. The CM scale covers different domains of shoulder function (pain, activities of daily living, range of motion and power), punctuating each of them; it ranges from 0 to 100, with higher scores indicating better function.

EuroQol-5D-3L (European Quality of Life), a generic score developed to describe health-related quality of life (34) will also be assessed preoperatively, at 6, 24 and 48 weeks postoperatively. This score includes five health domains: mobility, self-care, usual activities, pain / discomfort and anxiety / depression; each domain has 3 levels: no problem; some problems and extreme problems. In addition, the EuroQol-5D-3L has a visual analog scale where the participant assigns a value between zero and one hundred to his or her own health condition (35). At the end of its application, EuroQol-5D-3L will provide a unique numerical value that can be used for longitudinal comparison between two time periods (pre and postoperative, for example).

## **Secondary Outcomes**

Clinical outcome will also be assessed by the Simple Shoulder Test (SST), validated for Portuguese (36), preoperatively and at 6, 24 and 48 weeks after the procedure. SST is a simple, quick and widely used questionnaire for shoulder function measurement; consists of 12 dichotomous questions answered by the patient himself. Each positive answer (yes) is given a score; at the end of the questionnaire the percentage of positive answers (score) is made, and the higher the percentage, the better the shoulder function. Other outcomes measured will be VAS (visual analogue pain scale) at hospital discharge, 1, 2, 6, 24 and 48 weeks after the intervention. This scale allows pain intensity to be measured with maximum interobserver reproducibility; it consists of a 10 cm straight line with the ends determining the limits of pain sensation (no pain; worst pain ever experienced); the distance between zero (no pain) and the patient's demarcation defines the intensity of pain. Complications and failures of the proposed methods will also be assessed.

Failures will be characterized as need for additional surgical procedure and / or change of the initially proposed procedure.

After the 48th week all patients will be submitted to Magnetic Nuclear Resonance (MRI) of the operated shoulder to evaluate the integrity and healing of the repair performed.

## Statistical Planning

Descriptive analyzes of variables will be based on absolute frequencies and percentages for categorical variables and summary measures as means and standard deviations or medians and quartiles, as well as minimum and maximum values for numerical variables (37). Clinical scores will be represented by individual profile graphs separately by surgical technique group.

The groups will be compared for the presence of categorical clinical outcomes (failures, complications and healing integrity) by Chi-square or Fisher's exact tests, depending on the distribution observed after data collection.

For inferential analysis of numerical clinical outcomes, mixed models will be used and, if the normal distribution is not adequate, generalized mixed models will be used (38). The models will have time effects (preoperative, 6, 24 and 48 weeks after intervention), surgical technique group (open repair or arthroscopic repair) and the interaction effect between time and group. The size of the lesion (smaller than three cm or larger than three cm) will also be included in the models as a control variable, seeking to avoid possible biases.

The analyzes will be performed with the aid of the SPSS program (39), considering a significance level of 5%.

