## **Participants**

Patients participating in the study will be recruited and evaluated at the Shoulder and Elbow Surgery Center of Excellence at Alvorada Moema Hospital, a referral center for the treatment of shoulder and elbow injuries, and at [name] Municipal Hospital (M'Boi Mirim). Both hospitals will be co-participants in the project in question. Patients will undergo clinical evaluation, plain radiography and magnetic resonance imaging to confirm the diagnosis of rotator cuff injury. At this moment, the type of lesion will be evaluated, as well as its size, retraction (REF) and the degree of fatty infiltration of the muscular belly, according to the Goutallier classification (REF). The lesions will be classified as small (<1cm); moderate (1-3cm); large (3-5cm) or very large (> 5cm) (30). All patients will undergo examinations and preoperative clinical evaluation.

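### Healing integrity is tested without adjustment for lesion size, the plan's own control variable; adjusting is a near-free improvement to a valid test of a secondary outcome

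*Combined protocol and SAP*

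**What the plan says.** The Secondary Outcomes section has every patient undergo MRI after week 48 "to evaluate the integrity and healing of the repair performed". Statistical Planning then compares the "categorical clinical outcomes (failures, complications and healing integrity) by Chi-square or" Fisher's exact test, the choice between the two tests depending on the observed distribution. No covariate or stratum is named.

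The next paragraph of the same section sets a different rule for the scores: "For inferential analysis of numerical clinical outcomes, mixed models will be used". In those models lesion size, split at three centimetres, "will also be included in the models as a control variable, seeking to avoid possible biases".

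Lesion size is a true baseline variable. The Participants section, describing the diagnostic work-up with radiography and MRI, states: "At this moment, the type of lesion will be evaluated, as well as its size, retraction". It also defines four size classes, with cut-points at 1, 3 and 5 cm. The Allocation and Randomization section describes a computer-generated list in sealed opaque envelopes and mentions no stratification by lesion size.

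**The concern.** The sponsor considered lesion size able to bias the comparison of scores and adjusted for it there. The comparison that looks at the repaired lesion itself is left unadjusted, and no reason is given. Size is not described as a stratum in the randomisation either, so nothing in the design or the analysis protects the healing comparison from a chance difference in lesion size between the arms.

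Two things are at stake. If lesion size predicts healing, an unadjusted test has less power than one that uses it. And if one arm happens to receive more large tears, the crude difference in healing mixes lesion size with technique. Healing is the only structural outcome in the plan.

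**Working it through.** **The plan's own sample size.** Inputs from Sample Size Estimate: difference 10.4 points, SD 15, 90% power, 5% significance (taken as two-sided), 10% loss. Standardised difference: 10.4/15 = 0.693. Normal approximation: n = 2 × (1.960 + 1.282)² / 0.693² = 43.7, so 44 per arm. The t-test needs 44.7, so 45 (power 90.2%). Then 45/0.9 = 50. The stated figures reproduce. They concern Constant-Murley only; no power is stated for healing.

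**Assumptions for healing** (none is in the documents): 45 MRIs per arm; a share of tears over 3 cm; a non-healing risk in small and in large tears; a common odds ratio (OR) between techniques within size strata. The risk in the worse arm is p′ = OR × o / (1 + OR × o), with o = p/(1 − p). At OR 3.3, 15% becomes 0.582/1.582 = 37% and 45% becomes 2.70/3.70 = 73%, so the assumed effect is large.

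**Tests compared by simulation**, with unstratified allocation:
- Pearson chi-square without continuity correction (Fisher's test was not simulated).
- Cochran-Mantel-Haenszel (CMH), X² = (Σ(aₖ − Eₖ))² / ΣVₖ over the two size strata, where aₖ is the number not healed in one arm and Eₖ, Vₖ are its hypergeometric mean and variance.
- The same statistic with 0.5 subtracted from |Σ(aₖ − Eₖ)| (corrected CMH).

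Power at OR 3.3:

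| Non-healing, small / large | Share large | Chi-square | CMH | Corrected CMH |
|---|---|---|---|---|
| 15% / 45% | 30% | 66% | 70% | 61% |
| 15% / 60% | 30% | 58% | 67% | 58% |
| 10% / 60% | 40% | 47% | 61% | 50% |
| 15% / 30% | 30% | 70.5% | 70.5% | – |
| size not prognostic | – | 77.2% | 76.5% | – |

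At OR 2, in the first three scenarios, power is 20–27% for chi-square, 25–29% for CMH (a gain of about 1 to 5 points) and 17–21% for corrected CMH. A separate run at OR 3 and 4 with other risks gave gains of about 2 to 16 points when size was prognostic and −1 to 0 when it was not.

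**Type I error averaged over randomisations.** About 5% for both chi-square and CMH; about 2.5% for corrected CMH.

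**Type I error given an imbalance.** Take 18 versus 10 large tears of 45: 40% versus 22%, a gap of 17.8 points. With no technique effect, the expected crude difference is the gap times the risk difference between sizes:
- 15% / 45%: 0.178 × 0.30 = 5.3 points; chi-square rejects in 8.3% of trials.
- 15% / 60%: 0.178 × 0.45 = 8.0 points; chi-square rejects in about 11%.
- CMH rejects in about 5% in both.

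**How likely that imbalance is.** With 30% large tears, the difference in counts has SD √(2 × 45 × 0.3 × 0.7) = 4.35. A difference of at least 8 in either direction has a chance of about 8% (7.5/4.35 = 1.72 SD with continuity adjustment); at least 5, about 30%.

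**The case against.** The strongest reply is that nothing here is wrong. An unadjusted test of randomised groups is valid, and giving categorical outcomes one rule and numerical outcomes another is not a contradiction. This stands. A reader might infer from the 8–11% figure that the planned test inflates the false-positive rate. It does not: that rate applies only after an unlucky draw, one with about an 8% chance, and across all draws the rate is about 5%.

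A reader might also infer that power is always lost without adjustment. The documents do not support this. They give no healing rate, no share of large tears and no association between size and healing; that healing is closely tied to size is an assumption, suggested only by the plan's use of size as a control variable. With a weaker association (15% / 30%) the gain is nil.

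Two further replies stand. OR 3.3 is a large effect; at OR 2 healing is poorly powered with or without adjustment. And healing is a secondary outcome: the scores named as primary are numerical and so fall under models that already carry lesion size, and the study's goal is cost-effectiveness. No primary conclusion depends on this test.

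Finally, a stratified test can make matters worse if the continuity-corrected form is used: 61%, 58% and 50% against 66%, 58% and 47% for chi-square. That objection is met by naming the uncorrected test.

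What remains is that the covariate is already collected, the plan already treats it as important, and adjustment costs almost nothing if chosen in advance. If added only after an imbalance is seen, it will look data-driven.

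**Conclusion.** The point holds as a worthwhile but optional improvement to a secondary analysis; the planned test is not an error. Assuming 45 MRIs per arm and an odds ratio of 3.3, uncorrected stratification by lesion size is worth about 4 to 15 points of power where size strongly predicts non-healing, nothing where it predicts weakly, and minus about 1 point where it does not predict at all. It also keeps the error rate near 5% when the arms happen to differ in lesion size, where the unadjusted test can reach 8% to 11%. All of these figures rest on assumed risks. They show the range of benefit and do not predict this trial's result. Adjustment would not make healing an adequately powered outcome, and the sample size for Constant-Murley is unaffected.

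**What to change.** In Statistical Planning, pre-specify for healing integrity either a Cochran-Mantel-Haenszel test without continuity correction, stratified by lesion size (3 cm split), with its common odds ratio, or a logistic regression with group and lesion size. The logistic option was not simulated here. State explicitly that the continuity-corrected Mantel-Haenszel statistic will not be used, and check which version the SPSS output prints. Report a size-standardised risk difference beside the odds ratio.

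State which stratum holds a tear of exactly 3 cm; the present split into smaller or larger than three centimetres leaves it in neither. Keep chi-square or Fisher's exact test for failures and complications if events are few.

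Cost: a few sentences in the plan, before outcome data are seen; no new data, patients or software. The downsides are that the odds ratio becomes conditional on lesion size, which is why the standardised risk difference is needed, and that about 1 point of power is lost if size does not predict healing.

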## **Allocation and Randomization**

After eligibility assessment, all patients will be informed about the nature and purpose of the study and will only be included in the randomized distribution after signing the informed consent form. Patients will be consecutively allocated to one of two proposed treatment methods: open rotator cuff repair or arthroscopic rotator cuff repair. Allocation will be made according to instructions contained in opaque and sealed envelopes that will be numbered according to the computer generated randomization list (<http://www.randomizer.org>). The sealed, opaque envelope containing the method to be applied will be attached to the patient record. A person not associated with the study will open the envelope before the intervention and after the anesthetic technique is applied.

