## Sample Size Estimate

The sample size estimate was obtained to detect differences between the open and arthroscopic repair groups in relation to the primary outcome of the study, Constant-Murley Score (CM) instrument after the intervention.

Kukkonen's et. al study (40) estimated the clinically important minimal difference in CM score in 10.4 points in patients with rotator cuff rupture after three months of surgical treatment by the arthroscopic method.

The estimated sample size of 45 patients per group, 90 patients in total, would reach 90% power to detect a 10.4 point difference between groups in the CM instrument postoperative score with standard deviation of up to 15 points with significance level of 5% using a t-Student test. Predicting a loss of around 10% at 12 months of follow-up, we aimed to recruit 50 patients in each group.

The sample size estimate calculations were performed with the aid of the PASS software (41).

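### Free improvement: name the week-48 group difference as the one primary Constant-Murley (CM) test, and adjust it for the preoperative CM already collected, with an unstructured covariance

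*Combined protocol and SAP*

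**What the plan says.** All references are to the combined protocol and SAP.

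- **Primary outcomes.** CM "will be measured preoperatively at 6, 24 and 48 weeks after the intervention". The Abstract and Statistical Planning show that this means one preoperative and three postoperative measurements. No visit is called primary. A later sentence in the same section, that a score "can be used for longitudinal comparison between two time periods (pre and postoperative, for example", is about EQ-5D-3L, not CM.
- **Statistical Planning.** "The models will have time effects (preoperative, 6, 24 and 48 weeks after intervention), surgical technique group", plus the group-by-time interaction. Lesion size (below or above 3 cm) "will also be included in the models as a control variable, seeking to avoid possible biases". It is the only covariate. The section names no decisive contrast, no covariance structure across visits and no constraint on the preoperative group means. If normality is inadequate, generalized mixed models replace the normal ones.
- **Sample Size Estimate.** 45 per group "would reach 90% power to detect a 10.4 point difference between groups in the CM instrument postoperative score", using a t-test with SD up to 15. Week 48 appears only by implication: "Predicting a loss of around 10% at 12 months of follow-up". The target is a published difference, "in 10.4 points in patients with rotator cuff rupture after three months of surgical treatment", and CM is not measured at three months in this trial.
- **Allocation and Randomization.** A person outside the study "will open the envelope before the intervention and after the anesthetic technique is applied". The preoperative score therefore precedes disclosure of the allocation.

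**The concern.** Two things are left unused or undecided.

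First, a model with group, time and interaction offers several group comparisons: the difference at week 6, 24 or 48, the overall interaction, the group main effect and the change from before surgery. They answer different questions with different power. Unless one is named in advance, the choice can be made after the results are seen.

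Second, allocation is revealed only after the preoperative CM is taken, so the preoperative group means are equal in expectation by design. The planned model estimates a separate preoperative mean for each group and makes no use of this. Adjustment would give a narrower interval for the same patients and visits.

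**Working it through.** **Inputs from the Sample Size Estimate.** Difference 10.4 points, SD 15, 45 evaluable per group, 5% level, 10% loss. **Assumed, not in the documents:** correlation r between preoperative and week-48 CM, equal SDs before and after surgery, complete data unless stated, and an effect of 10.4 present at week 48. Power is from the noncentral t, two-sided.

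**1. The plan's own figure.** SE = 15 × √(2/45) = 3.16; noncentrality 10.4/3.16 = 3.29; df 88. Power is 90.2%, and 44 per group gives 89.5%, so 45 is the smallest size reaching 90%. 45/0.90 = 50. Both figures reproduce. The 95% half-width is t(0.975, 88) × 3.16 = 6.28 points.

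**2. Week-48 difference from the planned model.** A generalized least squares calculation with four visits, exchangeable correlation and complete data gives SE 3.16 at r = 0.2, 0.3, 0.5 and 0.7. The preoperative score contributes nothing to this contrast, and power stays at 90.2%.

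**3. Week-48 difference adjusted for preoperative CM.** Residual SD = 15 × √(1 − r²), df 87.

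| r | Residual SD | SE | Power | Half-width |
|---|---|---|---|---|
| 0.2 | 14.70 | 3.10 | 91.3% | 6.16 |
| 0.3 | 14.31 | 3.02 | 92.6% | 6.00 |
| 0.5 | 12.99 | 2.74 | 96.4% | 5.44 |
| 0.7 | 10.71 | 2.26 | 99.5% | 4.49 |

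Multiplying the variance by 1 + 1/(2n − 4) = 1 + 1/86, to allow for chance baseline imbalance, gives 91.0/92.4/96.2/99.5%, and 89.9% at r = 0. With complete data, the four-visit model with equal preoperative means has the same SEs as the covariate form when its covariance is right.

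**4. Other contrasts the same model offers.** Change from before surgery has SD 15 × √(2(1 − r)), df 88, and power 73.0/78.5/90.2/98.7% at r = 0.2/0.3/0.5/0.7. A group main effect averaged equally over the four times includes one time with no expected difference, so a constant postoperative effect of 10.4 appears as 10.4 × 3/4 = 7.8. If each postoperative visit were tested at 5% and any positive result accepted, which the plan does not propose, the false-positive chance would be 1 − 0.95³ = 14.3% under independence, or about 13.5% to 10.9% at between-visit correlations of 0.3 to 0.7 (assumed).

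**5. Why the covariance matters.** Suppose the constrained four-visit model is fitted with compound symmetry while postoperative scores correlate at 0.7 with each other (assumed) and at r with the preoperative score. The fit pools the six pairwise correlations: w = (3r + 3 × 0.7)/6. It then subtracts w times the preoperative difference. Since 15² × 2/45 = 10, the true variance is 10 × (1 − 2wr + w²), and the model reports 10 × (1 − w²).

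- At r = 0: w = 0.35, true SE √11.225 = 3.35, reported SE √8.775 = 2.96.
- At r = 0.5: w = 0.60, true SE √7.6 = 2.76, reported SE √6.4 = 2.53.

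The type I error of the week-48 test is about 8.2/8.2/8.0/7.1% at r = 0/0.2/0.3/0.5. In a simulation under the same assumptions, the unconstrained planned model kept 4.6-5.2%.

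**The case against.** **The plan already does enough.** The model is valid, its week-48 contrast has the planned power, and week 48 is a fair reading: it is the last visit, the loss allowance is at 12 months, and the Economic analysis section also runs to 48 weeks. All of this stands. It shows that the fix is small, not that a primary contrast has been declared.

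**The change contrast overstates the risk.** A reader might infer from the 73-79% figures that the trial is underpowered. The documents do not support that. The Sample Size Estimate targets a difference in postoperative score, and the pre-post sentence under Primary outcomes describes EQ-5D-3L. The low figures also need r below 0.5 with equal SDs. They show that the available contrasts differ, not what the trial's power is.

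**Lesion size and the repeated measures already capture the gain.** In part. If lesion size explained 10% of the variance (assumption), the planned contrast would have 92.9%. Adding preoperative CM, with lesion size explaining 10% of that too, gives 94.0/96.9/99.6% at r = 0.3/0.5/0.7. With 5 of 50 per arm missing only week 48 and exchangeable correlation (assumptions), the planned model has 90.7/91.2/91.9% and the adjusted one 92.9/96.6/99.6%. The gain shrinks but remains.

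**Adjustment can do harm.** It can, if equal preoperative means are imposed under too simple a covariance, as step 5 shows. This objection stands in full and shapes the fix.

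**Conclusion.** The point holds as a free improvement. No CM visit or contrast is declared primary, and the preoperative CM is collected but does not sharpen the week-48 comparison. The sample size stands, and nothing here makes the planned analysis invalid.

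Naming the contrast is worthwhile whatever r is. The gain from adjustment depends on r: about one power point and 0.1 CM points of half-width at r = 0.2, about six power points and 0.8 CM points at r = 0.5, and a loss of about 0.3 power points at r = 0. It is not guaranteed under every covariance choice. All figures assume SD 15 at both times and a 10.4-point effect at week 48, although the 10.4 comes from three months. They apply to the normal mixed model, not to the generalized fallback.

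**What to change.** **Statistical Planning.**

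- Name the one-degree-of-freedom group difference in CM at 48 weeks as the single primary CM test. Make the week-6 and week-24 differences, the overall interaction and the change contrasts supportive.
- Estimate that difference adjusted for preoperative CM in one of two ways: (a) model the 6-, 24- and 48-week scores with preoperative CM by visit as a covariate; or (b) keep all four visits and constrain the preoperative group means to be equal, so that group enters only at the postoperative visits. SPSS can fit (b) with the group indicator set to zero preoperatively.
- In either form, specify an unstructured covariance across visits and keep lesion size. State that form (b) will not be fitted with a random intercept or compound symmetry.
- Use the same form for EQ-5D-3L and the Simple Shoulder Test, which also have preoperative values.

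**Sample Size Estimate.** Name week 48 as the visit to which the calculation refers. The numbers need no change.

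**Cost.** SAP wording and a few extra covariance parameters: four visits need 4 × 5/2 = 10 in place of 2 under compound symmetry. There are no new data, visits or patients. Form (a) also leaves out patients with no postoperative score and does not estimate pre-post change directly; form (b) keeps both.
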